## **Study Overview**

Current smoking cessation pharmacotherapies are effective but most smokers fail to quit with even the best medications. This may occur because medication use strategies have not been developed in a methodologically principled manner, which had kept clinicians from using available medications most effectively. Some evidence suggests that innovative medication use strategies such as combining varenicline and nicotine replacement therapy may boost medication effectiveness markedly; however, because of a lack of systematic research, we do not know which innovative strategies are optimal.

Building on our recent NHLBI-funded publication in *JAMA* that described the modest effectiveness of varenicline pharmacotherapy, the proposed research will use a factorial design to evaluate two different medication use strategies on their ability to markedly enhance varenicline effectiveness in a large cohort of current smokers. Smokers (N=1250) will be randomly assigned to one of two levels for each of two factors: 1) an Adjuvant factor (varenicline + placebo patch versus varenicline + nicotine patch), and 2) a Duration factor (12 versus 24 weeks of active medication). Thus, this factorial design yields a "standard" varenicline treatment (12 weeks of active varenicline and 12 weeks of placebo varenicline + 24 weeks of placebo patch), and 3 *enhanced* treatments: 1) 12 weeks of active varenicline and 12 weeks of placebo varenicline + 24 weeks of active patch, 2) 24-weeks of active varenicline + 24 weeks of placebo patch, and 3) 24 weeks of active varenicline + 24 weeks of active patch. Both treatment modifications, longer duration therapy and use of a nicotine replacement therapy (NRT) adjuvant, have produced some quite promising effects. However, in both cases these modifications have been little researched, their effects are not *consistently* positive, and they have not been implemented in a potentially optimal manner. We will implement each modification in an innovative manner designed to enhance its effectiveness. In addition, all participants will be given counseling that supports adherent medication use and that is readily translatable to healthcare settings. The scientific rigor of this work will be enhanced by the use of placebo medication, a large sample, and a factorial design. The latter will allow us to test both the main and interaction effects of the experimental factors. We will also be able to compare each enhanced treatment with standard 12-week varenicline-only therapy to determine whether any of these medication use strategies significantly enhances treatment effectiveness. Outcomes will include long-term smoking abstinence (52 weeks), cost-effectiveness, adverse events, and withdrawal severity. This design will allow us to evaluate two major pharmacotherapy strategies (an NRT adjuvant, extended duration) that yield four distinct varenicline-based treatments. Specific aims of this research are:

**Specific Aim 1:** To determine whether varenicline pharmacotherapy is enhanced by either a nicotine replacement adjuvant (i.e., patch NRT) or extended medication duration (i.e., 24 vs. 12 weeks postquit). The effects of these pharmacotherapy strategies will be reflected in main effects for both experimental factors, and in direct comparisons of the enhanced varenicline conditions with standard 12-week varenicline-only. The primary outcome will be 52-week biochemically confirmed smoking abstinence (7-day point-prevalence).

**Specific Aim 2:** To determine the effects of the varenicline conditions on additional critical outcomes such as 23-week point prevalence and prolonged abstinence, smoking cessation milestones (abstinence, latency to lapse, and lapse-relapse latency), cost-effectiveness, withdrawal severity, and adverse events. The variables that mediate and moderate (e.g., genotype) the effects of the different pharmacotherapies will also be identified.

**PROTOCOL**  
“Quitting Using Intensive Treatment Study (QUITS)”  
PI: [name] and [name] ; UW-CTRI Grant:

This research will determine whether two highly promising modifications to varenicline treatment, use of a nicotine patch adjuvant and extended 24-week duration, produce superior smoking outcomes when they are used either individually or together. Despite their promise, the tested modifications have never been experimentally evaluated relative to standard varenicline pharmacotherapy. Thus, this innovative research will produce novel evidence regarding how best to help smokers quit, and thereby address the leading cause of preventable mortality and morbidity related to cardiovascular and pulmonary diseases.

### **Recruitment & Study Entry**

We will recruit participants via multi-media methods (i.e., TV, radio, newspapers and newsletters and other print media, flyers, referral cards, minority outreach, emails to UW employees, social media such as Facebook, and earned media), which we have previously used very successfully. Within 1 week, respondents will be called, screened, and potentially eligible smokers will be scheduled to attend a group orientation session. At the Orientation session, interested individuals will be introduced to the study, have a chance to ask questions and provide written informed consent. Participants will complete a final inclusion/exclusion assessment and complete the baseline assessments. Randomization to a treatment condition will also occur at the Orientation (see Table 2), with stratification on sex, site, dependence, and race.

### **Inclusion/Exclusion**

Participants must: plan to stay in the area for the next 12 months, ability to read and write in English, smoke on average  $\geq 5$  cigarettes per day over the last 6 months, be  $\geq 18$  years old, desire to quit smoking but not be engaged currently in cessation treatment, report no use of pipe tobacco, cigars, snuff, e-cigarettes or chew in the last 30 days, have reliable phone access, willing and able to use both nicotine patch and varenicline, access to transportation to come to our clinic and, if female, not be pregnant and be using an acceptable birth control method/ method to prevent pregnancy. Smoking will be biochemically confirmed via a carbon monoxide breath test at the first visit. Preparticipants must blow a CO of  $\geq 5$  ppm to continue. Exclusion criteria include: current treatment for schizophrenia or a psychotic disorder; suicidal ideation in the past 12 months; history of suicidal attempts within the last 10 years; on dialysis or being told you have severe kidney disease; hospitalization for a stroke, heart attack, congestive heart failure, uncontrolled diabetes mellitus within the past year; history of seizure within the last year, currently taking Wellbutrin, Zyban, or Bupropion (Contrave is a weight-loss drug that has Wellbutrin in it) for reasons other than to quit smoking or taking to help quit smoking and not willing to stop for duration of the study; currently using any form of nicotine replacement (e.g., nicotine patch, nicotine gum, nicotine lozenge) or using Chantix or varenicline and not willing to stop for duration of the study; had a reaction to the nicotine patch that prevented them from continuing to use it; or currently participating in another smoking cessation study.

Even though we screen out participants who are pregnant, plan to become pregnant, nursing, or are unwilling to take steps to avoid pregnancy, there is a chance that a participant eligible at consent could become pregnant later. She would then be considered part of a vulnerable group. Given the longitudinal nature of the research, a participant who becomes pregnant after enrolling will be given the choice of whether to 1) continue in the study (for counseling and other assessments) and agree to immediately stop taking study meds for the remaining duration of the study and return any unused medications, OR 2) withdraw. No further

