**Phone Follow-Up Assessments:** These person-to-person phone assessments will occur at 4, 8, 11, 17, 23, 39, and 52 weeks post-TQD (Table 2). Data will be gathered on daily smoking, new quit attempts, use of other cessation medication, potential mediators (e.g., withdrawal, affect, cigarette liking/effects, stressors, cue exposure, motivation), use of any nicotine product, medication use, and adverse events. Participants claiming abstinence at the 6- and 12-month calls will be invited to a visit for biochemical testing and short questionnaire on CO exposure to confirm abstinence self-report via exhaled CO. If participants claim abstinence from cigarettes but blow a 6 or greater on the CO breath test at the Week 52 Follow-Up Visit, we will ask the participant if they will give us a saliva sample to test for cotinine. This will allow us to be more certain that these participants have not been smoking cigarettes (as evidenced by cotinine-free saliva or saliva with low levels of cotinine). At the 12-month call all participants will be asked to estimate the likelihood that their pill and their lozenge contained active medication.

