**PROTOCOL**  
**"Quitting Using Intensive Treatment Study (QUITS)"**  
 PI: [name] and [name] ; UW-CTRI Grant:

**Smoking Outcome Measures:** As per Society for Research on Nicotine and Tobacco recommendations, we will analyze abstinence at 52 weeks (primary) and 23 weeks using two abstinence measures to enhance scientific rigor: (1) 7-day point-prevalence (CO-confirmed self-report of abstinence from smoking for 7 days before and including the follow-up day: CO cutoff ≤ 5ppm) and (2) prolonged (a continuous abstinence measure that ignores smoking in the first

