**Table 2. Schedule of Study Activities**

	Pre-Cessation	Treatment Phase						Phone Follow-up				
		V1	C1	V2	V3	C2	C3	C4	C5	C6 	C7	C8 
Week	Orientation	Wk - 2	-1	TQD	2	4	8	11	17	23	39	52
Screening & Informed consent	X											
Randomization	X											
Pre-cessation counseling		X	X									
Cessation counseling				X	X	X	X					
Exhaled CO	X	X		X	X					X 		X 
Short questionnaire on CO exposure	X	X		X	X					X 		X 
Smoking status	X	X	X	X	X	X	X	X	X	X	X	X
Blood sample for DNA/RNA and cotinine		X										
Non-cigarette nicotine use	X	X		X		X	X			X		X
Baseline questionnaires	X	X										
IVR assessments	X	X	X	X	X							
Treatment mechanisms assessment 		X	X	X	X	X	X	X	X	X	X	X
Medication provision		X		X			X					
Medication use assessment			X	X	X	X	X	X	X	X	X 	
Adverse events			X	X	X	X	X	X	X	X	X	X

If participants claim abstinence during this assessment call, they will be invited to an in-person visit to provide biochemical verification of abstinence (CO assessment).

Treatment mechanisms include withdrawal, affect, fatigue, cigarette liking/effects, stressors, cue exposure, motivation, and self-efficacy.

Timeline follow back only

week post-quit). Per our intention-to-treat data analysis plan, any randomized smoker who does not provide biochemically confirmed evidence of abstinence will be counted as a smoker; multiple imputation also will be performed in secondary analyses to further enhance scientific rigor. A daily smoking calendar will permit determination of lapse/relapse latencies for survival and milestones analyses. In order to enhance *scientific transparency*, we will post all assessment instruments and, ultimately, de-identified data, online (e.g., the UW-CTRI website; average of 7,000 hits/month over last year from 17,387 visitors), so that other researchers can use our de-identified data and instruments (see detail in Data Sharing Plan).

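### A CO reading of exactly 5 ppm meets both the entry rule for smoking and the outcome rule for abstinence, so an unchanged reading cannot refute a false abstinence claim from someone who entered at 5 ppm

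*Combined protocol and SAP*

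**What the plan says.** On entry, the Inclusion/Exclusion section states: "Smoking will be biochemically confirmed via a carbon monoxide breath test at the first visit". It then sets the value: "Preparticipants must blow a CO of $\geq 5$ ppm to continue".

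On outcome, Smoking Outcome Measures defines 7-day point-prevalence abstinence, primary at Week 52 and also analysed at Week 23, as "CO-confirmed self-report of abstinence from smoking for 7 days before and including the follow-up day: CO cutoff ≤ 5ppm".

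On who is tested at follow-up, footnote 1 of Table 2 reads: "If participants claim abstinence during this assessment call, they will be invited to an in-person visit to provide biochemical verification of abstinence".

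On the back-up test, Phone Follow-Up Assessments provides for a saliva cotinine request "If participants claim abstinence from cigarettes but blow a 6 or greater on the CO breath test at the Week 52 Follow-Up Visit". No such back-up is described for Week 23.

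On later conduct, the COVID-19 update under Compensation stops the in-person Week 52 confirmation visits.

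**The concern.** The two rules use the same measurement and share one value. By the trial's own abstinence standard, a reading of 5 ppm does not establish smoking, yet it is accepted as doing so at entry. For a participant admitted at that value, a later reading of 5 shows no change, but it counts as confirmation of abstinence.

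The primary outcome is presented as biochemically confirmed, and the purpose of confirmation is to remove false claims. For someone who entered at 5 ppm and reads 5 again, it removes none, and the result rests on self-report. Wrongly confirmed participants would raise the abstinence rate in every arm and slightly shrink the differences between arms. The Week 23 outcome uses the same cutoff.

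Low entry readings are plausible, since the section admits people who "smoke on average $\geq 5$ cigarettes per day over the last 6 months". The documents do not show how often they occur.

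**Working it through.** The plan gives no figure for this point, so there is none to reproduce. The check is of the thresholds, followed by an illustrative size.

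**1. Thresholds on whole-ppm readings**

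| Rule | Source | Readings that satisfy it |
|---|---|---|
| Entry, smoking confirmed | Inclusion/Exclusion | 5, 6, 7, ... |
| Abstinence confirmed | Smoking Outcome Measures | 0 to 5 |
| Cotinine requested, Week 52 | Phone Follow-Up Assessments | 6, 7, 8, ... |

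Entry and abstinence overlap at {5} only. Abstinence and the cotinine trigger do not overlap, so a reading of 5 is never sent for cotinine. If either inequality were strict (entry > 5, or abstinence < 5), the overlap would be empty.

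**2. What else misclassification needs**

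The participant must be smoking, must report seven days without smoking, must attend the visit and must read 5 ppm or less. Anyone who reports smoking counts as a smoker at any CO.

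**3. Illustrative number affected**

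Table 4 predicts 78 + 106 + 100 + 140 = 424 abstainers of 1,248, or 34%. That leaves 66% non-abstinent, and 0.66 × 1,250 = 825.

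Let *q* be the share who entered at 5 ppm and *r* the share of non-abstainers who falsely claim abstinence. Neither is in the documents; both are assumed. It is also assumed that *q* applies equally to non-abstainers and that the later reading is again 5 ppm or less. Then *s* = *q* × *r*, and the number wrongly confirmed is 825 × *s*.

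| *q* | *r* | *s* | Wrongly confirmed |
|---|---|---|---|
| 1% | 2% | 0.0002 | 0.2 |
| 5% | 10% | 0.005 | 4.1 |
| 10% | 20% | 0.02 | 16.5 |

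**4. Effect on the comparisons**

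With the same *s* in every arm, an abstinence rate *p* becomes *p* + (1 − *p*)*s*, and a difference is multiplied by (1 − *s*). At *s* = 0.02:

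- Duration: 29.5% becomes 30.91% and 38.5% becomes 39.73%. The difference falls from 9.0 to 8.82 points.
- Adjuvant: the difference falls from 10.9 to 10.9 × 0.98 = 10.68 points.

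Power for two proportions, two-sided 0.05, is Φ{[|p₂ − p₁| − 1.96√(2p̄(1 − p̄)/n)] / √([p₁(1 − p₁) + p₂(1 − p₂)]/n)}.

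| Comparison | n per group | *s* = 0 | *s* = 0.02 |
|---|---|---|---|
| Duration | 625 | 0.920 | 0.905 |
| Adjuvant | 625 | 0.983 | 0.977 |
| 24-week combination vs 12-week varenicline only | 312 | 0.9996 | 0.9992 |

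The plan states .88 for Duration, which this formula does not return from Table 4. Only the change between the two columns matters here.

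**The case against.** The strongest reply is that the outcome is a confirmed self-report, not a CO value. A reader might infer that a 5 ppm entrant is confirmed abstinent without any change. The documents do not support that, because the claim of abstinence comes first and CO only checks it.

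A reader might also infer that the check can never fail in this group. That would require CO to stay at 5 from one entry reading to Week 52, and nothing in the plan says it does. A continuing smoker who once blew 5 may later blow 6 or more. Conversely, someone who entered at 6 or 7 may later read 5, so separating the cutoffs does not cure weak discrimination near the boundary.

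Nor does the plan treat 6 ppm as proof of smoking: that reading prompts a request for cotinine. And a minimum of 5 cigarettes a day does not show that anyone enters at exactly 5 ppm; the Protection of Human Subjects section gives a minimum of 10.

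Finally, the 66% includes people counted as smokers because they were never tested. They cannot be wrongly confirmed, so step 3 leans high on that input. The COVID-19 update is a larger threat to Week 52 confirmation than one shared value.

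All of this stands, and it limits the consequence. It does not remove the overlap, which no passage resolves. The update does not cure it either: the cutoff still governs Week 23 and any Week 52 visits that were held.

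**Conclusion.** The point holds as a minor inconsistency. The overlap itself is certain and is confined to the single value 5 ppm. For a participant who entered there, an unchanged reading cannot refute a false abstinence claim, and no cotinine test follows.

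The size is unknown. The range of about 0.2 to 16.5 participants rests on assumed values for the share at 5 ppm and the rate of false claims. The same rules apply in all four arms, so the error should be mainly non-differential: a slight inflation of rates and a slight dilution of differences. The documents give no basis for inferring a bias towards any treatment.

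**What to change.** Make the cutoffs mutually exclusive, for example by requiring an entry CO above 5 ppm (6 or more). This changes one figure and costs a few more screen failures among light smokers.

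For participants already enrolled, a new entry rule does nothing. Keep all of them in the intention-to-treat analysis, report by arm how many entered at exactly 5 ppm, and add a sensitivity analysis that leaves them out. Run it for the Week 23 outcome and for those Week 52 outcomes that were actually CO-confirmed. Define the group by the reading that decided eligibility, since Table 2 schedules exhaled CO at both Orientation and V1. This needs no new data, and because the reading precedes treatment, the exclusion does not depend on treatment effects.

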**PROTOCOL**  
“Quitting Using Intensive Treatment Study (QUITS)”  
PI: [name] and [name] ; UW-CTRI Grant:

medications will be given to this study participant while in the study.

Incarcerated individuals will not be enrolled in this study. However, given the longitudinal nature of the research, participants could be incarcerated for periods during their participation. If study staff learn that a participant is incarcerated at a time point before or at their Week 8 phone call, the participant will be withdrawn from the study. If study staff learn that a participant is incarcerated subsequent to Week 8, the participant will not be withdrawn unless that incarceration will take them beyond the study period. In that case, staff will not contact the participant while incarcerated and will not provide any treatment (counseling or medication) nor conduct any assessments during the period of incarceration. Services and assessments will be re-initiated if the participant is released at a later study time point.

## **Study Design**

All participants (N=1250) will receive at least 12 weeks of V plus counseling that emphasizes adherent medication use. Participants will also be randomized to one level of each of the two factors: 1) an Adjuvant factor: active P vs. placebo P; and 2) a Duration factor: 24 vs. 12 weeks of active medication.

## **Assessments**

*Baseline:* These will constitute covariates for analyses (e.g., smoking dependence, heaviness, history), characterize the cohort, and capture baseline levels of potential mediators of treatment effects. They also will permit assessment of constructs that will be used to develop an optimal, patient-centered treatment algorithm. The surveys (gathered at Visit 1: Table 2; associated references provide psychometric data) will include: (1) The Smoking History Questionnaire, which provides accurate information about lifetime smoking cessation treatment history, family smoking, environmental exposure, and psychiatric history; (2) The Brief Wisconsin Smoking Dependence Motives questionnaire (Brief WISDM); (3) The Fagerstrom Test for Cigarette Dependence (FTCD); (4) Alcohol use and problems assessed with a quantity-frequency measure for the past week; (5) The Wisconsin Predicting Patients' Relapse questionnaire (WI-PREPARE) which may inform algorithm development; (6) The 5-trial Adjusting Delay Task to assess ability to delay reward; (7) interview about changes to make to quit successfully; and (8) the Depression, Anxiety and Stress Scales (DASS-21) to assess current symptoms of depression, anxiety and stress. In addition, a psychiatric history will be gathered that assesses prior diagnoses and treatment for psychiatric disorders including substance use (as per). Blood will be drawn (about 2 tablespoons) for DNA extraction and genotyping as in prior UW-CTRI RCTs and for serum cotinine analysis. Breath carbon monoxide will be assessed.

*DNA assessments.* Samples for DNA analysis will only be taken from those providing consent for this. As outlined in the Biological Samples protocol supplement, blood will be drawn for samples of DNA for genetics, DNA for methylation (Madison site only), and RNA(Madison site only). DNA for genetics will be extracted by the UW Biotechnology Center. All three samples will be relabeled at the UW Biotechnology Center with DNA IDs/ barcodes, which allows connecting additional data secured from participants at later visits but does not contain HIPAA identifiers that can be connected back to the study. Samples will be stored at both the UW Biotech Center (DNA for genetics @-80°C) and CTRI Madison (DNA for methylation and RNA @-20°C) until shipped in batches to Washington University. Banking will occur at Washington University in St.

**PROTOCOL**  
“Quitting Using Intensive Treatment Study (QUITS)”  
PI: [name] and [name] ; UW-CTRI Grant:

Louis within a genetics research facility. In this facility samples will remain labeled with only DNA IDs. All study information is stored in secure computer databases at that location.

In addition, we plan that DNA data and associated phenotype information from study participants will be sent to an NIH GWAS center, where stringent controls are in place for security of genomic information and any study information related to the samples. GWAS will utilize these samples, combined with others submitted to the repository, for additional research questions

**Note: Participants can withdraw their DNA consent by request to the study PI**

**IVR Assessments:** To enhance scientific rigor, participants will provide nightly data (via phone keypad responses to voice prompts or complete an on-line survey) for a total of 31 days (3 days prior to starting treatment, 14 days during pre-cessation treatment, 14 days post-target quit day; see Table 2). Each report will take about 3-4 minutes to complete. Reports will assess mood, anhedonia, withdrawal, cessation fatigue (post-quit), cue exposure and reactivity, and tobacco and medication use with brief items used in our prior successful research. Medication effects and reasons for not using medications will also be assessed. All reports will end with a reminder of the number participants can call to discuss any concerns they have about study medications. Nightly IVR data collection reduces error that might arise from memory decay and recall biases. This time frame should capture key pharmacotherapy effects, the peak of withdrawal, and most lapse occurrences. These assessments will capture potential treatment mechanisms/mediators, treatment effects, and variables related to safety/side effects. Our procedures entail minimal burden (~3-4 min/day) and yield high (~80%) completion rates. Those who report having difficulty maintaining a stable phone/email service will be provided phones to take IVR phone calls.

**Phone Follow-Up Assessments:** These person-to-person phone assessments will occur at 4, 8, 11, 17, 23, 39, and 52 weeks post-TQD (Table 2). Data will be gathered on daily smoking, new quit attempts, use of other cessation medication, potential mediators (e.g., withdrawal, affect, cigarette liking/effects, stressors, cue exposure, motivation), use of any nicotine product, medication use, and adverse events. Participants claiming abstinence at the 6- and 12-month calls will be invited to a visit for biochemical testing and short questionnaire on CO exposure to confirm abstinence self-report via exhaled CO. If participants claim abstinence from cigarettes but blow a 6 or greater on the CO breath test at the Week 52 Follow-Up Visit, we will ask the participant if they will give us a saliva sample to test for cotinine. This will allow us to be more certain that these participants have not been smoking cigarettes (as evidenced by cotinine-free saliva or saliva with low levels of cotinine). At the 12-month call all participants will be asked to estimate the likelihood that their pill and their lozenge contained active medication.

